Participants in all 4 groups who provide informed consent will be asked to complete a contact information sheet (in which they will be asked to provide name, telephone number, address and email address) and a baseline assessment packet that includes the following measures (see Baseline Questionnaire Packet for actual measures). Given the length of the questionnaire packets at baseline and follow-up, participants will be asked to stop and take a 5-minute break after approximately 25-30 minutes to reduce fatigue and increase the likelihood of gathering quality data. Participants will also be asked to complete a computerized attentional bias task, in which they are shown a series of neutral and sad or neutral and happy faces for a brief duration (e.g., 500-1000ms). The images are removed and one image is replaced with either an O or Q. The participant is asked to indicate on a response box which letter replaced the image. This task is a test to determine whether the subject has a negative attentional bias. They will also be asked to complete a second computer task in which they are shown a series of faces, starting from neutral, that eventually morph into happy, angry, or sad faces. Participants are asked to indicate (by pressing a key or response box) when they can identify the emotion and then are asked to identify the emotion.

- 1) **Demographics and psychiatric history** measure created for this study and includes information about sex, age, relationship status, income, and individual and family current and past psychiatric diagnostic status.
- 2) **Modified Differential Emotion Scale (MDES)** is a scale that includes 20 different positive and negative emotional states. Respondents are asked to indicate how often in the past month they have experienced each emotion.
- 3) **Self-Other Four Immeasurables Scale** is a 16 item scale designed to measure kindness, compassion, joy, and acceptance toward self and others. Respondents use a 5 point Likert scale to indicate how often they have experienced the thoughts, emotions, and behaviors in the past week.
- 4) **Ambiguous Situation** task consists of 10 statements that can be interpreted in either a positive/neutral or negative light. After reading each statement, the participant is asked to rank order 4 potential interpretations of the scenario they've just read in terms of how closely they resemble the scenario.

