- 13) **Rosenberg Self Esteem (RSE)** is composed of 10 statements regarding general notions of self perception. The respondent is directed to indicate how strongly he/she agrees with the statement (i.e., I take a positive attitude toward myself) using a 7 point Likert scale.
- 14) **Scale of Physical Symptoms** consists of a list of 9 physical symptoms including shortness of breath, runny or congested nose, and chest or heart pain. Participants indicate how often they've experienced such symptoms over the past month using a 7 point scale, ranging from Not at All to Frequently.
- 15) **Pittsburgh Sleep Quality Inventory (PSQI)** is a self report measure designed to assess sleep difficulties, sleep quality, and to gather data regarding bedtimes, waking times, and number of hours slept.
- 16) **Social Connectedness Scale (SCS)** is an 8 item scale that assesses an individual's sense of connection and disconnection to society, peers, etc. Two additional items have been added to the original scale to assess connection/disconnection to nature and to a spiritual/religious community.
- 17) **MOS Social Support Scale** is composed of 19 statements describing possible supports (e.g., advice, information, help with chores) to which the respondent is asked to indicate how often each is available to him/her.
- 18) **Perceived Stress Scale (PSS)** asks respondents to indicate how often in the past month they have felt stressed, nervous, unable to cope, etc., using a 5 point Likert scale.
- 19) **Life Events Scale (LES)** requires individuals to indicate which of the possible positive negative life events he/she has experienced during the most recent 6 months.
- 20) **Emotion Socialization Scale of the Emotions as Child Scale (EAC)** was modified slightly by Garside and colleagues to include both mother and father responses to the respondent's emotional displays as a child. Using a 7 point Likert scale, participants indicate how often each parent responded to sadness, for example, with 15 different possibilities.
- 21) **Emotion Regulation Questionnaire (ERQ)** directs participants to indicate how strongly they agree or disagree with 10 statements describing ways people typically regulate or manage emotion.
- 22) **Ten Item Personality Inventory (TIPI)** is a very brief measure of personality. Participants are asked to indicate the extent to which each of the statements describes them.

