H5: Participants in the PS and PTPSS conditions will demonstrate significant changes in behavioral indicators of attentional shifts. We anticipate participants in the active experimental conditions will a) take increasingly more photographs over the course of the intervention and b) will include more social behavior as the focal point.

Supplementary Analyses

H6, exploratory: In order to inform future implementation and potential mechanisms of change, we will examine photographic content. We also anticipate changes in the quality of the photographs over the course of the intervention for the participants in both active experimental conditions. It is possible that the photographic content would be judged by independent raters to be increasingly positive over the course of the intervention. Alternatively, it is plausible that as the participant's ability to attune to the positive cues in the environment

develops, the capacity to find joy in even the most mundane objects/moments will be evident in photographs judged by independent raters to have less objectively rated positive appeal.

H7: Depressive symptoms will moderate the associations between intervention participation and daily positive affect, life satisfaction, and perceived social support, such that participants with higher levels of pre-intervention symptoms will show larger improvements in outcomes in the intervention conditions.

H5b and H6 are straightforward between-groups analyses, for which we will use ANOVA to test for significant differences between groups on the outcomes of interest. H1-H3 and H5a will be tested using mixed-factor ANOVA, with condition as a between-subjects factor and the within-subjects factor being pre-intervention measure of the outcome of interest included as predictors of the post-intervention outcome (e.g., perceived social support). Planned contrasts will probe for significant differences in effects between the experimental conditions and each control condition, as appropriate. H7 will be tested using two additional predictors, the main effect of the individual difference of interest (e.g., depressive symptoms) as well as the interaction between the individual difference and condition. H4 (mediation) will be tested using the most up-to-date evidence for bootstrapping estimates (see Hayes; Preacher & Hayes, 2008).

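### H5b is planned as an unadjusted ANOVA although plausibly prognostic scales are collected before randomisation; prespecified baseline adjustment is a cheap efficiency gain of unknown size

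*Combined protocol and SAP*

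**What the plan says.** The analysis paragraph that follows H7 under Supplementary Analyses treats the hypotheses differently.

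- **H5b and H6:** "H5b and H6 are straightforward between-groups analyses, for which we will use ANOVA to test for significant differences between groups". No covariate is named.
- **H1-H3 and H5a:** a mixed-factor ANOVA with the "pre-intervention measure of the outcome of interest included as predictors of the post-intervention outcome".
- **H7:** the individual difference of interest, such as depressive symptoms, enters as a main effect and as an interaction with condition.

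H5b, listed under Mediators of Change, expects that participants in the experimental conditions "will include more social behavior as the focal point". H6 is introduced as "H6, exploratory: In order to inform future implementation and potential mechanisms of change, we will examine photographic content", and its text anticipates changes in photograph quality over the course of the intervention.

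Section 3, Testing Procedure, lists the baseline packet. It includes the MDES, which "is a scale that includes 20 different positive and negative emotional states", the BDI-II, the Social Connectedness Scale, the MOS Social Support Scale, which "is composed of 19 statements describing possible supports", and the TIPI, which "is a very brief measure of personality". The same section places randomisation after the packet and the computer tasks. It asks three of the four groups for photographs; the passive control group is asked for none.

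**The concern.** Photographs are taken only after randomisation, so the H5b and H6 outcomes have no baseline value of their own. That explains why these two hypotheses cannot follow the H1-H3 model. It does not mean that nothing measured at baseline can be used: ANCOVA needs only a baseline variable that predicts the outcome. A student who feels well connected may photograph people more often in any arm. If so, stable differences in sociability stay in the error term of the planned ANOVA, and the arm contrasts are less precise than they could be without collecting anything further.

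The stake is the precision of H5b, which is not labelled exploratory, and to a lesser degree that of H6, which is.

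**Working it through.** **The plan's own figure.** There is none to reproduce. The documents give no significance level, power, effect size, SD or dropout rate, and no derivation of the sample size.

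**Inputs from the documents.** About 240 participants (section 2, Identification of Subjects); four groups, three of which take photographs (section 3); baseline scales completed before randomisation (section 3).

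**Assumptions not in the documents.** Equal allocation, so 240/4 = 60 per arm and 3 × 60 = 180 with photographs; no dropout; one outcome value per participant; two-sided 5% level; 80% power for the detectable difference; a true difference d = 0.5 SD for the power figures; correlation r between covariate and outcome from 0 to 0.5.

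**Formulas.**
- Residual variance factor: 1 − r².
- Equivalent participants per arm: 60/(1 − r²).
- Detectable difference in SD units: (1.960 + 0.842) × √[(1 − r²)(1/n₁ + 1/n₂)].
- Power: Φ(d/√[(1 − r²)(1/n₁ + 1/n₂)] − 1.960).

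For 60 v 60 and r = 0, √(2/60) = 0.1826. The detectable difference is 2.802 × 0.1826 = 0.511 SD, and power is Φ(0.5/0.1826 − 1.960) = Φ(0.779) = 78.2%.

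| Assumed r | 1 − r² | Equivalent n per arm | Detectable difference, 60 v 60 | Power, 60 v 60 | Power, 120 v 60 |
|---|---|---|---|---|---|
| 0 | 1.00 | 60.0 | 0.511 | 78.2% | 88.5% |
| 0.1 | 0.99 | 60.6 | 0.509 | 78.6% | 88.8% |
| 0.2 | 0.96 | 62.5 | 0.501 | 79.8% | 89.8% |
| 0.3 | 0.91 | 65.9 | 0.488 | 81.9% | 91.2% |
| 0.4 | 0.84 | 71.4 | 0.469 | 84.8% | 93.2% |
| 0.5 | 0.75 | 80.0 | 0.443 | 88.5% | 95.5% |

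The last column pools the two experimental arms against Document This!. A noncentral t calculation for 60 v 60 with one covariate gives nearly the same power: 77.7% unadjusted, then 78.2%, 79.4%, 81.5%, 84.4% and 88.2%.

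**Cost if the covariates are unrelated to the outcome.** With N = 180, three groups and k covariates, the variance of a contrast is multiplied by about (180 − 3 − 1)/(180 − 3 − k − 1).
- k = 1: 176/175 = 1.006, a rise of about 0.6%.
- k = 2: 176/174 = 1.011, a rise of about 1.1%.

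The break-even R² is k/176. That is 0.006 for one covariate (r about √0.0057 = 0.075) and 0.011 for two (multiple correlation about √0.0114 = 0.107). Two covariates with a joint correlation of only 0.1 would therefore gain nothing.

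**The case against.** The strongest reply is that the plan contains no error here. Unadjusted ANOVA is a valid analysis of a randomised comparison. A reader might infer that chance imbalance in sociability or mood distorts the planned contrast. The documents do not support that: imbalance arising from randomisation is already allowed for in the standard error and the type I error rate. This part of the reply stands in full.

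A second reply is that the gain may be negligible. A questionnaire score need not correlate well with rater-coded photograph content, and at r = 0.1 to 0.2 power rises by only 0.4 to 1.6 points. This also stands. It limits the claim but does not remove it, because the cost is about as small as the smallest gain.

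A third reply concerns H6, and it has most force. H6 is exploratory and is about change over the intervention, which an ANOVA on one value per person does not test. H6 also leaves the direction open: rated positivity may rise, or may fall as participants come to find joy in mundane things. A simple slope on baseline mood is then not an obvious choice. The closing paragraph of the document plans exploratory growth curve analyses, and in a within-person analysis stable differences between students largely drop out. A reader might infer that H6 needs the adjustment as much as H5b; the documents do not bear that out. The introduction to H5 also speaks of changes, but the analysis paragraph classes H5b as a between-groups comparison, and that is how it is taken here.

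Finally, the picture-taking instructions differ by arm, so the covariate slope may differ too. Under randomisation a common-slope ANCOVA still estimates the average arm difference in a sample of this size, but unequal slopes could reduce the gain.

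**Conclusion.** The point holds as a low-severity efficiency improvement, mainly for H5b. The planned analysis is valid but may lose some precision. It would be tempting to say that precision is definitely being lost. The documents cannot show this, since the loss depends on a correlation that they do not give.

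Under the stated assumptions the gain for 60 v 60 is under 2 power points at r = 0.1 to 0.2, and 3.7 points at r = 0.3 (81.9 − 78.2) to 10.3 points at r = 0.5 (88.5 − 78.2). No evidence in the documents favours one end of that range. Dropout or unequal allocation would change the absolute power figures, but not the proportional fall in error variance for a given r. For H6 adjustment is optional, and secondary to fitting a model that addresses change over time.

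**What to change.** Before any photographs are coded, replace the H5b part of the analysis sentence with a statement along these lines: H5b will be analysed by ANCOVA with one summary value per participant, across the three photograph-taking arms, with condition as the factor and the baseline Social Connectedness Scale score as covariate. Baseline MOS Social Support may be named as a second covariate. State that the covariates are fixed in advance and that none will be added or dropped after the data are seen.

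For exploratory H6, the baseline MDES positive score may be added in the same way, ideally in a model that includes time.

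The cost is one or two sentences in the plan, no new data, and one or two degrees of freedom out of about 180 participants. If the covariates prove unrelated to photograph content, precision falls slightly, as shown in the working.

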- 23) **Test of Self Conscious Affect – 3 (TOSCA-3)** is a scenario based measure composed of 16 scenarios of potential positive and negative occurrences in work and social arenas of life. It is designed primarily to assess shame and guilt responses but also includes pride. The respondent is asked to respond to several questions following the scenarios indicating the likelihood of reacting in certain ways. Sixteen of the 32 scenarios are presented at baseline.
- 24) **Irritability Question – One question designed to assess participant irritability at the conclusion of completing the questionnaires was added.**

Following completion of the questionnaire packet and the computerized tasks, the participant will be randomized to 1 of 4 groups. All groups will be provided a packet of instructions to guide their participation in the coming weeks, and the packet will be reviewed with the participant by someone on the research team (see Appendix A). Participants in the 3 picture taking groups will also be provided instructions to create a login to the research drive if they do not have an account and will be provided instructions regarding how to upload their photographs to the research drive.

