In brief, both the Picture This! and the Picture This! Plus Social Sharing groups groups will be asked to utilize their Smartphones to take photographs on a daily basis for 21 days. The participants in the Picture This! and Picture This! Plus Social Sharing Group are asked to notice and then photograph events/situations/people/places/cues that elicit positive emotion (i.e., joy, awe, gratitude). They are asked to take at least two photographs each day. Participants in the active Document This! control group are also asked to take at least two photographs each day for 21 days that they feel is a good representation of their daily lives. The passive control group is not asked to take any pictures over the 21 day period. Each day, participants in the active conditions are asked to upload the photographs taken that day to a Google Drive accessed only by study staff. Participants will not have access to other participants' photographs, only their own. Participants will be informed in the consent form that submission of photographs poses a risk to confidentiality because the photos may include "self-shots" (photos they have taken of themselves) or photos of other things that could be linked back to them personally if by chance the trained and ethically-bound research assistants happen to know the participants.

At the conclusion of the study, participants will be asked in a separate Photo Release Form if they would provide permission to study personnel to use their photographs in research manuscripts, grant proposals, educational presentations, and other media presentations (see Appendix E).

All 4 groups are asked to provide an active email address and instructed to complete a short series of questions nightly that will be emailed to them from our lab email Gmail address. The email will include a link to a survey powered by Google Docs, which includes the MDES, modified to ask participants about feelings experienced during the past 24 hours (see above for description), and 6-9 additional questions designed specifically for this study (see Appendix D for questionnaires designed for both the active and control groups). The 3 active condition groups are also asked to complete a nightly savoring exercise and to answer several questions about the exercise via a link to the exercise sent to their email (see Appendix D).

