- 11) Carolina Empirically Derived Mindfulness Inventory (CEDMI)
- 12) Brief Satisfaction with Life Scale (BSWLS)
- 13) Rosenberg Self Esteem
- 14) Scale of Physical Symptoms
- 15) Pittsburgh Sleep Quality Inventory (PSQI)

- 16) Social Connectedness Scale (SCS)
- 17) MOS Social Support Scale (MOS)
- 18) Perceived Stress Scale (PSS)
- 19) Life Events Scale (LES) Respondents will be asked to consider the time that has elapsed since baseline (which should be approximately 4-5 weeks).
- 20) Emotion Regulation Questionnaire (ERQ)
- 21) TOSCA-3 with 16 novel scenarios
- 22) Irritability Question
- 23) Intervention Assessment – 5 questions created by the project staff to assess participant satisfaction with prescribed exercises and to elicit suggestions for improvement.

The following compensation/incentive schedule for completing questionnaires and participating in the study will be utilized:

- Participants who complete the baseline questionnaire packet and computer tasks will be compensated \$10 or be provided with class credit via the psychology subject pool.
- Participants who complete the exit questionnaire packet and computer tasks will be compensated \$19 or be provided with class credit via the psychology subject pool.
- Participants will be compensated \$1/day for completing the nightly online questions for a potential total of \$21.
- Participants will be compensated \$1/each weekly survey completed for a potential total of \$3.

Hypothesized Outcomes

H1: Participants in the Picture This! (PT) and Picture This! Plus Social Sharing (PTPSS) conditions will evidence increased well-being as indexed by measures of: a) depressive symptoms, b) positive affect, c) savoring beliefs, d) mindfulness e) life satisfaction, f) self esteem, g) gratitude, h) physical health and sleep quality, and i) perceived social support, relative to participants in the active control and no picture control conditions.

H2: Participants in the Pictures This! Plus Social Sharing will demonstrate greater improvement in perception of social support than those in any other condition.

Mediators of Change.

H3: Participants in the PT and PTPSS conditions will show significant changes in automatic cognitive processes including attentional biases, interpretational biases, and cognitive style assessed via behavioral tasks and self report.

H4: Changes in the aforementioned cognitive processes will account for the positive changes in mental and physical health.

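### The pre/post analysis rule cannot be applied to H5a, and for H1-H3 it names a mixed-factor ANOVA while describing an ANCOVA

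*Combined protocol and SAP*

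**What the plan says.** The combined protocol and SAP deals with four hypotheses in one sentence of the analysis paragraph that follows H7. It states that "H1-H3 and H5a will be tested using mixed-factor ANOVA", with condition between subjects, and then describes "the within-subjects factor being pre-intervention measure of the outcome of interest included as predictors of the post-intervention outcome". The next sentence adds: "Planned contrasts will probe for significant differences in effects between the experimental conditions and each control condition, as appropriate". The paragraph goes on: "H7 will be tested using two additional predictors", namely the moderator and its interaction with condition.

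H5a predicts that participants in the two experimental conditions will "take increasingly more photographs over the course of the intervention". H2 predicts that the social-sharing condition "will demonstrate greater improvement in perception of social support than those in any other condition".

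The Testing Procedure section gives the order of events: "Following completion of the questionnaire packet and the computerized tasks, the participant will be randomized to 1 of 4 groups". Picture-taking then runs for 21 days, and "participants in the active conditions are asked to upload the photographs taken that day to a Google Drive". The passive control group is asked for no pictures. The weekly surveys on taking and sharing photographs also fall in this period.

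The closing paragraph of the document returns to time. It says that daily photographs may be rated for positivity and social connection, that these may rise over time (with a cross-reference to H5a), and that exploratory growth curve analyses will be done.

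**The concern.** In a mixed-factor ANOVA with two visits, baseline and exit are both responses, the within-subjects factor is time, and the effect of interest is condition by time. A baseline value used to predict the exit value belongs to a different model, ANCOVA. The sentence gives the name of the first and the description of the second, and does not say which effect is tested. Two analysts could follow it in good faith and run different tests on the same H1-H3 outcomes.

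For H5a neither model can be built from the stated ingredients. The hypothesis is about a trend within the intervention, so the repeated factor it needs is day or week. The sentence supplies a pre-intervention value and a post-intervention value instead.

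At stake are a hypothesis with no workable confirmatory analysis (H5a), and, for H1-H3, some power and the assurance that the model was fixed before the data were seen.

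**Working it through.** **H5a: can the rule be applied?**

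1. The rule needs a pre-intervention measure of the outcome. The outcome is the number of photographs taken for the study. Baseline comes first, then randomisation, then the instructions and picture-taking.
2. The baseline list has 24 items. None is described as a photograph count. The packet itself is not in the public text, so this is judged from the list.
3. The weekly surveys come after randomisation and cannot serve as baseline.
4. The rule uses condition with four levels. One of the four, the passive control group, is not asked for photographs.
5. The closing paragraph does not supply a replacement. Its time trend concerns positivity and social connection rather than number of photographs, and its growth curves are labelled exploratory.

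The named procedure is not itself the obstacle. With week as the within-subjects factor, a mixed-factor ANOVA fits H5a. As a check, daily counts were simulated under an assumed distribution (15% zero, 68% two, 11% three, 6% four, varying by person). Over 10,000 trials with no trend, a linear week trend on weekly totals was significant in 4.9% within 120 experimental participants, and in 5.3% for the difference from 60 in Document This!.

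**H1-H3: how far apart are the two readings?**

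The plan gives no figure to reproduce. From the documents: about 240 participants and four conditions. Assumed, because the documents do not give them: equal allocation (240/4 = 60 per arm), no dropout, equal SDs of 1 at both visits, d = 0.4, two-sided 0.05, baseline-exit correlation r of 0.5 to 0.8, and one 60 vs 60 contrast analysed alone.

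- Change-score variance: 2(1 − r).
- ANCOVA residual variance: 1 − r².
- Ratio, ANCOVA to change: (1 − r²) / [2(1 − r)] = (1 + r)/2.
- ANCOVA size per arm that matches a change-score test on 60: 60 × ratio.
- Power: noncentral t with noncentrality 0.4 × √(60/2) / √variance. At r = 0.5 this is 2.19/1 = 2.19 for change and 2.19/0.866 = 2.53 for ANCOVA.

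| r | Change variance | ANCOVA variance | Ratio | Matching n per arm | Power, change | Power, ANCOVA |
|---|---|---|---|---|---|---|
| 0.5 | 1.00 | 0.75 | 0.75 | 45 | 58.4% | 70.9% |
| 0.7 | 0.60 | 0.51 | 0.85 | 51 | 80.1% | 86.1% |
| 0.8 | 0.40 | 0.36 | 0.90 | 54 | 93.0% | 95.2% |

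Both tests were also run on the same simulated data, 40,000 trials per cell:

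| r | Readings disagree on significance (d = 0.4) | At least one significant (d = 0) |
|---|---|---|
| 0.5 | 18.9% | 7.2% |
| 0.7 | 9.2% | 6.9% |
| 0.8 | 3.3% | 6.5% |

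Each test alone stayed at 4.8% to 5.1% when d = 0.

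With exit SD equal to k times baseline SD, the ratio is k²(1 − r²)/(1 + k² − 2rk). At k = 1.25 and r = 0.8 it is 0.5625/0.5625 = 1.00, so nothing is lost. At k = 0.8 and r = 0.5 it is 0.48/0.84 = 0.57, a larger loss than under equal SDs.

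**The case against.** The best defence for H1-H3 is that the intent is plain. The sentence speaks of predictors of the post-intervention outcome, and the H7 sentence adds further predictors to the same model. Both point to ANCOVA, in which case only the label is wrong and no precision is lost. Even if the named procedure is run, it is a valid analysis under randomisation, and preferring ANCOVA is a matter of efficiency. This stands, and it makes the H1-H3 part a clarification. It does not settle the text: the procedure name and the phrase about a within-subjects factor point the other way, and no other section decides between them.

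The power figures rest entirely on assumed inputs, and the gap is small at high correlation. That also stands. The 6.5% to 7.2% false-positive figures apply only if both tests are run and the favourable one is kept; nothing in the documents says that this will be done.

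For H5a, the closing paragraph shows that the authors had time trends in mind. That softens the criticism, but exploratory work on other features of the photographs does not replace the stated test.

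A reader might go further and infer that the H1-H3 analysis is invalid, that mixed-factor ANOVA is the wrong method for H5a, or that the trial certainly holds no baseline photograph count. The documents support none of these: both H1-H3 models are sound, week or day as the repeated factor makes the ANOVA fit, and the questionnaires are not visible.

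**Conclusion.** The H5a rule is wrong as written: going by the listed measures, it asks for a baseline that is not collected, and for a comparison across four conditions of which one is not asked to take photographs. This conclusion rests on the order of events and the baseline list, and needs no assumed figures.

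For H1-H3 the sentence is ambiguous between two valid models and leans towards ANCOVA. The precision loss is zero if ANCOVA was meant. If condition by time is run, the loss is usually real: under the stated assumptions it is equivalent to working with 45 to 54 participants per arm instead of 60, or about 2 to 13 points of power. It can vanish or grow when the two visits have different SDs. The plan should be corrected before analysis; nothing in the trial's conduct has to change.

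**What to change.** Replace the single sentence with separate statements.

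- **H1 and H2.** *Each exit score will be analysed by ANCOVA with condition (four levels) as factor and the baseline score on the same measure as covariate; planned contrasts are tested on the baseline-adjusted exit means.* List the contrasts: each experimental condition against each control condition for H1 (or the two experimental conditions pooled, if that is meant), and the social-sharing condition against each of the other three for H2.
- **H3.** H3 names no comparator. Use the same model for the between-condition contrasts, and state that this tests a difference from the control conditions. If change within a condition is also intended, report the baseline-to-exit change in the two experimental conditions separately.
- **H7.** Add baseline depressive symptoms and their interaction with condition to this model for life satisfaction and perceived social support. For daily positive affect, first define one outcome from the nightly MDES, for example each participant's mean over the 21 days, with the baseline MDES positive score as covariate.
- **H5a.** Take it out of the pre/post sentence. Test weekly photograph totals in the three picture-taking conditions by mixed-factor ANOVA, with week (1 to 3) as the within-subjects factor and condition by week. Report the time trend within the two experimental conditions, which is the hypothesis as stated, and separately its difference from Document This!. State that uploads are used as the record of photographs taken.

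The cost is wording only. Baseline and exit scores, nightly reports and daily uploads are already collected.
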